8.3.2 Follow-up visit/Visit 2a

The following should be completed at the follow-up visit 14 days (+7 days) after the Baseline/Initial treatment/Day 1 visit (Table 1):

- Perform visual function assessments (see Section 7.6).
- Perform palpability assessments (see Section 7.4).
- Perform sensory tests (see Section 7.2).
- Perform functionality tests (see Section 7.3).
- Evaluate changes in facial hair growth in the treated area (see Section 7.5).
- Review of the Subject Diary. Remind subject to complete the Subject Diary daily and bring it to the next on-site visit.
- Obtain post-treatment photographs of the chin area.
- Interview the subject regarding any concomitant therapies.
- Interview the subject regarding any AEs that have occurred since last visit.
- Remind subject of the next scheduled on-site visit (Visit 3) 1 month (4 weeks; +7 days) after the baseline visit (Visit 1b).

8.3.3 Follow-up visit/Optional touch-up/Visit 3

The following should be completed at the follow-up visit 1 month (4 weeks; +7 days) after the Baseline/Initial treatment/Day 1 visit (Table 1):

- Assessments to be performed prior to optional touch-up if treatment will be given:
 - Assessment of GCRS – Treating Investigator (see Section 6.3).
 - Pre-treatment pain assessment using the NPS (prior to application of any anesthetic) (see Section 7.1).

Effective date: 2023-05-24 22:48

- Perform visual function assessments (see Section 7.6).
- Perform palpability assessments (see Section 7.4).
- Perform sensory tests (see Section 7.2).
- Perform functionality tests (see Section 7.3).
- Evaluate changes in facial hair growth in the treated area (see Section 7.5).

CCI

- Obtain pre-treatment photographs of the chin area.
- Interview the subject regarding any concomitant therapies.
- Interview the subject regarding any AEs that have occurred since last visit.

If touch-up is to be performed, the following should be confirmed/performed:

- Assess whether optimal aesthetic result has been achieved (as agreed by the Treating Investigator and subject) and determine whether optional touch-up is appropriate.
- Re-confirm eligibility (inclusion and exclusion criteria) – prior to treatment.
- Perform UPT for all females of childbearing potential (prior to treatment). Test result must be negative for the subject to be eligible for treatment.
- Optional touch-up treatment – subjects will be injected with the assigned study product. After injection, the following should be performed:
 - Immediately following injection, subject should complete the post-treatment pain assessment using the NPS (see Section 7.1). This should be completed before any post-injection therapies are provided.
 - Approximately 30 minutes after injection, perform visual function assessments - post-treatment (see Section 7.6).
 - Record all concomitant medications/procedures used prior, during or after the injection session.
 - Record the following injection details:
 - Date and time of completed injection
 - Lot number
 - Number of syringes used
 - Volume of study product used
 - Needle or cannula used for supraperiosteal or subcutaneous injections
 - Injection method and depth of injection
 - Additional local or topical anesthesia used
 - Evaluate for device deficiencies. If any device deficiency is noted, complete the form as specified in Section 7.13.4.

CCI

CONFIDENTIAL

Effective date: 2023-05-24 22:48

Effective

- Evaluation of post-injection AEs by Treating Investigator.
- Schedule the 72 hours (± 24 hours) follow-up telephone call (Visit 3a), the follow-up visit (Visit 3b) at 14 days (2 weeks; +7 days) after touch-up and the follow-up visit (Visit 3c) at 1 month (+7 days) after touch-up as well as (Visit 4) at 3 months (± 14 days) after touch-up.

If touch-up is not to be performed:

- Schedule the next on-site visit (Visit 4), 3 months (12 weeks; ± 14 days) after the Baseline/Initial treatment/Day 1 visit (Visit 1b).

8.3.4 Telephone call/Visit 3a (Subjects that received touch-up)

The following should be completed at the telephone contact 72 hours (± 24 hours) after touch-up (Table 1):

- Interview the subject regarding the Subject Diary completion and reported events since receiving treatment. Remind subject to complete the Subject Diary daily and bring it to the next on-site visit.
- Interview the subject regarding any concomitant therapies.
- Interview the subject regarding any AEs that have occurred since receiving treatment. If AEs are reported, notify the Investigator immediately and determine whether subject should return to the study center for an unscheduled visit. The Investigator should assess all reported AEs in a timely manner.
- Interview the subject regarding when (in hours after treatment) the subject felt comfortable returning to social engagements (public/social appearances) exemplified as returning to business office or other public workplace, having dinner in a public restaurant, attending a social event/gathering such as dinner party, etc.
- Remind the subject of the next scheduled on-site visit (Visit 3b), 14 days (2 weeks; +7 days) after the touch-up treatment (Visit 3).

8.3.5 Follow-up visit/Visit 3b (Subjects that received touch-up)

The following should be completed at the follow-up visit 14 days (+7 days) after touch-up treatment (Table 1):

- Perform visual function assessments (see Section 7.6).
- Perform palpability assessments (see Section 7.4).
- Perform sensory tests (see Section 7.2).
- Perform functionality tests (see Section 7.3).
- Evaluate changes in facial hair growth in the treated area (see Section 7.5).
- Review of the Subject Diary. Remind subject to complete the Subject Diary daily and bring it to the next on-site visit.
- Obtain post-treatment photographs of the chin area.
- Interview the subject regarding any concomitant therapies.

CONFIDENTIAL

Version: 4.0

Effective date: 2023-05-24 22:48

Effective date:

Effective

- Interview the subject regarding any AEs that have occurred since last visit.
- Remind the subject of the next scheduled on-site visit (Visit 3c), 1 month after the touch-up treatment (Visit 3).

8.3.6 Follow-up visit/Visit 3c (Subjects that received touch-up)

The following should be completed at the follow-up visit 1 month (+7 days) after touch-up treatment (Table 1):

- Perform visual function assessments (see Section 7.6).
- Perform palpability assessments (see Section 7.4).
- Perform sensory tests (see Section 7.2).
- Perform functionality tests (see Section 7.3).
- Evaluate changes in facial hair growth in the treated area (see Section 7.5).
- Review and collection of the Subject Diary.
- Obtain post-treatment photographs of the chin area.
- Interview the subject regarding any concomitant therapies.
- Interview the subject regarding any AEs that have occurred since receiving treatment.
- Remind the subject of the next scheduled on-site visit (Visit 4), 3 months (12 weeks) after the touch-up treatment (Visit 3).

8.3.7 Follow-up visits/Visits 4–6

The following should be completed at the follow-up visits at 3, 6 and 9 months (12, 24 and 36 weeks; ± 14 days) after last treatment (Table 1):

- Assessment of GCRS – Blinded Evaluator (see Section 6.3).

- Perform visual function assessments (see Section 7.6).
- Perform palpability assessments (see Section 7.4).
- Perform sensory tests (see Section 7.2).
- Perform functionality tests (see Section 7.3).

CONFIDENTIAL

Page 65 of 88

Version: 4.0

Effective date: 2023-05-24 22:48

- Evaluate changes in facial hair growth in the treated area (see Section 7.5).
- Obtain post-treatment photographs of chin area.
- Interview the subject regarding any concomitant therapies.
- Interview the subject regarding any AEs that have occurred since last visit.
- Schedule or remind the subject of the next on-site visits (as applicable); Visit 5 at 6 months (24 weeks; ± 14 days), Visit 6 at 9 months (36 weeks; ± 14 days) after last treatment.

8.3.8 Follow-up visit/End of study visit/Visit 7

The following should be completed at the end of study (EOS) visit at 12 months (48 weeks, ± 14 days) after last treatment (Table 1):

- Record subject's weight.
- Assessment of GCRS – Blinded Evaluator (see Section 6.3).

- Perform visual function assessments (see Section 7.6).
- Perform palpability assessments (see Section 7.4).
- Perform sensory tests (see Section 7.2).
- Perform functionality tests (see Section 7.3).
- Evaluate changes in facial hair growth in the treated area (see Section 7.5).
- Obtain post-treatment photographs of the chin area.
- Interview the subject regarding any concomitant therapies.
- Interview the subject regarding any AEs that have occurred since last visit.

9. STATISTICAL DESIGN AND ANALYSIS

9.1 General

A comprehensive Statistical Analysis Plan (SAP) with detailed description of all statistical analyses will be developed before database lock.

All study data will be listed in subject data listings.

All statistical analyses, including summary tables and data listings, will be performed using SAS. Confidence intervals (CIs) will be two-tailed and constructed at a confidence level of 95% unless

CONFIDENTIAL

Page 66 of 88

Effective

Version: 4.0

Effective date: 2023-05-24 22:48

Effective

Version: 4.0

otherwise specified. Statistical tests will be performed at a significance level of 5%, and p-values will be two-sided, unless otherwise specified.

Continuous endpoints will be summarized using descriptive statistics, e.g., number of subjects (n), mean, median, standard deviation (SD), minimum and maximum values. Categorical endpoints will be presented in frequency tables with number and percentage of observations for each level.

9.2 Analysis populations

The following analysis populations will be defined:

Intention to treat (ITT):

Includes all subjects who are randomized and will be analyzed according to the randomization scheme.

Per protocol (PP):

Includes all subjects in the ITT population who complete the primary endpoint assessment at 3 months after baseline or last treatment without any deviations considered to have substantial impact on the primary effectiveness.

Safety:

Includes all subjects who were treated with *Restylane Lyft with Lidocaine* or *Juvéderm Voluma XC* will be analyzed according to the as-treated principle.

The ITT population will be the primary population for all effectiveness analyses. If the PP population contains less than 90% of the subjects in the ITT, a sensitivity analysis of the primary effectiveness endpoint will be performed based on the PP population.

The safety analysis will be performed on the safety population.

The disposition of subjects will be presented in tables and/or figures as appropriate. The number of screened, randomized, treated, completed, and withdrawn subjects will be presented, as well as number of subjects in each analysis population set.

9.3 Demographics, baseline assessments, and subject characteristics

Demographic endpoints, baseline assessments, and subject characteristics will be presented based on the ITT analysis set using descriptive statistics by treatment, as appropriate.

9.4 Effectiveness analysis

9.4.1 Primary effectiveness analysis

The primary effectiveness analysis is test of non-inferiority of *Restylane Lyft with Lidocaine* to a comparator-control *Juvéderm Voluma XC* in the Intention to treat (ITT) and Per Protocol (PP) analysis sets, using the confidence interval (CI) approach.

The change from baseline in GCRS, as assessed by the Blinded Evaluator, will be analyzed using a mixed effect model with treatment as fixed effect and subject as random factor. The change from baseline at Month 3, after last treatment, will be the response variable.

Non-inferiority will be established if the upper limit of the Confidence Interval (CI) is below the non-inferiority margin of 0.5 units. Superiority will be declared if the upper limit is below 0. This

GALDERMA

Title
43USCH2208, Clinical Investigation Plan R Lyft Chin US

Doc id

MA-52558

Effective date: 2023-05-24 22:48

Effective date:

decision criterion is consistent with a gate-keeping strategy (testing for superiority following the test for non-inferiority) to maintain the overall type I error rate at 2.5%.

The null and alternative hypotheses are stated below.

Δ = the LS mean estimate of (Restylane Lyft with Lidocaine - Juvéderm Voluma XC), the statistical hypotheses to be tested are:

$H_0: \Delta \geq 0.5$

$H_1: \Delta < 0.5$

The primary variable is the Month 3 GCRS value minus the Baseline GCRS value. This change from Baseline measure indicates a favorable result for a subject if the value is negative. From the model a 95% confidence interval for the LS mean estimate of the treatment difference (Restylane – Control) is calculated. A negative value for the mean treatment difference is a favorable result for Restylane, and a positive value for the mean treatment difference is a favorable result for the Comparator.

9.4.2 Secondary effectiveness analysis

For the GCRS, a responder will be defined as a subject with at least 1 point improvement from baseline based on the GCRS. For a significant result, the two-sided p-value of the comparison of responder rates between the treatment groups at Month 3, 6, 9 and 12 using the Fisher's exact test. The estimates of the responder rate in each treatment group will be presented with corresponding CIs.

CCI

Effective

Version: 4.0

CONFIDENTIAL

Page 68 of 88

Effective date: 2023-05-24 22:48

9.6 Handling of missing data

Number of missing values will be summarized and reported as appropriate.

For ITT analysis of the responder rate based on the Blinded Evaluators' live assessment of the GCRS, at 3 months after last treatment, the analysis will be performed using multiple imputation (MI) as the primary imputation method.

Impact of missing data on the primary endpoint will be evaluated by performing sensitivity analysis based on the baseline observation carried forward (BOCF) method, and the observed cases in the ITT set.

All other effectiveness endpoints will be evaluated based on the observed cases in ITT.

Descriptive statistics of all safety data will be performed on observed cases in the Safety population.

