2. STUDY OBJECTIVES, ENDPOINTS AND HYPOTHESIS

2.1 Study objectives

2.1.1 Primary objective and endpoint

The primary objective of the study is to demonstrate non-inferiority of *Restylane Lyft with Lidocaine* versus *Juvéderm® Voluma™ XC* for augmentation of the chin region to improve the chin profile by comparing change from baseline in the Blinded Evaluator live assessment of the Galderma Chin Retrusion Scale (GCRS) at 3 months after last treatment.

Primary Endpoint:

Change from baseline in the Blinded Evaluators' live assessment using the GCRS at 3 months after last treatment.

GALDERMA

Title
43USCH2208, Clinical Investigation Plan R Lyft Chin US

Doc id

MA-52558

Effective date: 2023-05-24 22:48

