2.1.2 Secondary objectives and endpoints

To evaluate the effectiveness of *Restylane Lyft with Lidocaine* versus a comparator-control for augmentation of the chin region to improve the chin profile, for the defined endpoints:

1. Responder rate based on the Blinded Evaluators' live assessment using the GCRS at 3, 6, 9 and 12 months after last treatment.

A responder is defined as a subject with at least 1 grade improvement from baseline on the GCRS.

CCI

CCI

Effective

Version: 4.0

CONFIDENTIAL

Page 27 of 88

Effective date: 2023-05-24 22:48

Effective

[figure not shown]

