## 9.2 Secondary Effectiveness Analysis

Secondary effectiveness analysis will be evaluated based on the OC in ITT Population, unless otherwise indicated.

P-values obtained for any endpoint other than the primary will only be provided for ease of interpretation of results. All other secondary effectiveness analyses will be performed descriptively only.

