## 11 Statistical/Analytical Issues

### 11.1 Handling of Missing Data

The number of missing values will be summarized and reported as appropriate in all outputs. Calculations for all questionnaires will follow the methods specified in the specific sections of this SAP for the handling of the data.

For ITT analysis of the change from Baseline based on the Blinded Evaluator's live assessment of GCRS at Month 3 after last treatment (primary endpoint), the analysis will be performed using MI as the primary imputation method. Multiple imputation methods are specified in [Section 11.6](#).

Sensitivity analyses will be performed to evaluate the impact of missing data on the primary endpoint using BOCF, worst case, and observed cases as described in [Section 9.1.3](#).

All other effectiveness endpoints will be evaluated based on the OC in the ITT analysis set. Descriptive statistics of all safety data will be performed on OC in the Safety Population.

Galderma

Protocol number: 43USCH2208

Protocol V4.0

In the event the intensity, relationship, or seriousness of an AE is missing, the most severe value will be assigned. Intensity will be assigned to “Severe”, relationship will be assigned to “Related to Study Product and Study Procedure”, and seriousness will be imputed to SAE.

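### Protocol 9.6 and SAP 11.1 give multiple imputation to different Month 3 endpoints, SAP 15.2 declares neither change, and the Month 3 responder rate omits subjects the primary analysis keeps

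*Protocol*

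**What the plan says.** The primary endpoint (Protocol 2.1.1) is "Change from baseline in the Blinded Evaluators' live assessment using the GCRS at 3 months after last treatment". The first secondary endpoint (Protocol 2.1.2) is "Responder rate based on the Blinded Evaluators' live assessment using the GCRS at 3, 6, 9 and 12 months after last treatment", where a responder gains one grade or more.

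Protocol 9.6 opens its missing-data rule with the responder rate: "For ITT analysis of the responder rate based on the Blinded Evaluators' live assessment of the GCRS, at 3 months after last treatment", and for that analysis "the analysis will be performed using multiple imputation (MI) as the primary imputation method". It goes on: "Impact of missing data on the primary endpoint will be evaluated by performing sensitivity analysis based on the baseline observation carried forward (BOCF) method", together with an observed-case analysis. It then closes the effectiveness rules with "All other effectiveness endpoints will be evaluated based on the observed cases in ITT".

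The SAP is arranged differently. Section 11.1 gives multiple imputation (MI) to the Month 3 change from baseline, labelled as the primary endpoint, and then states "All other effectiveness endpoints will be evaluated based on the OC in the ITT analysis set". Section 9.2 says "Secondary effectiveness analysis will be evaluated based on the OC in ITT Population, unless otherwise indicated", and 9.2.1, which covers the responder rate, indicates nothing else. Section 11.6 describes MI for the primary analysis only. Section 15.2 lists two departures from the protocol: the Investigator Satisfaction Questionnaire, and running the per-protocol sensitivity analysis whatever the size of that population.

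**The concern.** The two documents give opposite missing-data rules for two results taken from the same scale, rater and visit, and the section meant to record such changes does not mention it. A reader of the final report could not tell whether the responder rate follows the plan.

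There is also a practical consequence. The primary analysis covers every randomised subject, while the responder rate covers only those with a Month 3 score. The two could then disagree partly because they describe different people. An observed-case rate is unbiased only if, within arm, being missing is unrelated to responding. For one group the SAP has already settled the outcome: subjects lost to follow-up who missed Month 3 and later re-enrolled are set to no change in the primary analysis (SAP 9.1.1 and 11.6). No change means non-responder, yet observed cases removes these subjects from the denominator.

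**Working it through.** **1. The texts side by side**

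| Blinded Evaluator GCRS endpoint | Protocol 9.6, read literally | SAP 9.2, 11.1, 11.6 | In SAP 15.2? |
|---|---|---|---|
| Month 3 change from baseline (primary) | Observed cases, as one of the other endpoints | MI | No |
| Month 3 responder rate (secondary) | MI | Observed cases | No |
| Months 6, 9, 12 responder rate (secondary) | Observed cases | Observed cases | Not needed |

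Both Month 3 rows change. The later visits agree.

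**2. The plan's own sample size.** Inputs from Protocol 9.11: margin 0.5, assumed disadvantage 0.1, SD 0.7, power 90%, two-sided 95% CI, 2:1 allocation.

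- Control n = (1 + 1/2) × SD² × (1.960 + 1.282)² / (0.5 − 0.1)² = 1.5 × 0.49 × 10.51 / 0.16 = 48.3, rounded up to 49.
- Investigational n = 2 × 49 = 98. Total = 147, which matches the plan.
- 147 / 0.85 = 172.9, so 173. The next multiple of 3 is 174, which also matches.

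**3. How many subjects the observed-case rate can omit.** The Protocol synopsis and SAP 3.2.3 allow about 15% loss at 3 months.

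- 0.15 × 116 = 17.4 and 0.15 × 58 = 8.7, together 26.1.
- Equivalently, 174 − 147 = 27 (18 and 9 at 2:1), and 27 / 174 = 15.5%.

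This is an upper bound. The allowance also covers subjects who are non-evaluable because of protocol deviations, and some of them may have a Month 3 score and stay in the observed cases.

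**4. Illustration of bias in one arm.** Let a fraction m of the arm be missing, let the observed rate be p, and let the missing subjects' rate be p − g. The rate over all randomised subjects is (1 − m)p + m(p − g) = p − mg, so observed cases overstates it by mg.

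- g = 10 points: 0.15 × 10 = 1.5 points.
- g = 20 points: 0.15 × 20 = 3 points.

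The documents give no value for g, and m = 0.15 is the upper bound from step 3. If mg is the same in both arms, the rate difference is unaffected.

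**5. Extreme bounds.** The documents give no responder rate, so assume 80% observed in both arms: 78/98 and 39/49, with 18 and 9 missing.

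- All missing fail: 78/116 = 39/58 = 67%. All missing respond: 96/116 = 48/58 = 83%.
- Difference (investigational − comparator): from 78/116 − 48/58 = −15.5 points to 96/116 − 39/58 = +15.5 points.
- With 6 and 3 missing (about 5%) and 80% observed, the range is −5.2 to +5.2 points.
- At 15.5% missing, assumed rates of 70% and 90% give −14.7 to +16.4 and −15.5 to +15.5 points.

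These are limits that no assumption about the missing subjects can exceed. They are not expected bias.

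**6. Re-enrolled subjects.** Each one adds 1 to the denominator and 0 to the numerator under the SAP's own rule. With the comparator figures above, one such subject moves 39/49 = 79.6% to 39/50 = 78.0%. The documents do not say how many there are.

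**The case against.** The strongest reply is that the protocol sentence is a slip. The sentence after it turns to missing data on the primary endpoint. Read literally, Protocol 9.6 also leaves the primary endpoint on observed cases, so its observed-case sensitivity analysis would merely repeat the main analysis. SAP 11.1 keeps nearly the same sentence and substitutes the change score, which looks like a correction. Protocol 9.4.2 also names Fisher's exact test for the responder rate at all four visits, which fits observed cases.

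This is plausible, and it counts against a reading that a reader might be tempted to make: that the SAP knowingly downgraded the secondary endpoint. The documents do not show intent. But a correction is still a change. On the slip reading, the method for the primary endpoint itself has moved without being declared, so SAP 15.2 needs an entry either way.

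Other replies carry weight:

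- SAP 9.1.3 reruns the primary analysis on observed cases, with baseline carried forward, and with worst-case imputation. A mean change on the same missing-data footing as the responder rate will therefore exist. The converse, a responder rate on the primary footing, will not.
- Imputation may recover little. Under SAP 3.2.4.1 the Blinded Evaluator scores at screening, baseline and then Month 3, so no earlier post-treatment score from that rater informs the imputed value.
- Secondary p-values are offered only as an aid to interpretation (SAP 9.2).

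These limit the size of the problem; they do not remove the conflict.

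**Conclusion.** The conflict stands: two Month 3 endpoints have exchanged missing-data rules between protocol and SAP, and neither change is declared. As written, the responder rate omits up to about 26 to 27 of 174 subjects whom the primary analysis keeps, among them any re-enrolled subjects whom the SAP treats as unchanged. For that last group the direction is known: relative to the SAP's own rule, leaving them out can only raise the rate.

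Beyond that group the size is modest and uncertain. The 1.5 to 3 points depend on an assumed gap of 10 to 20 points in one arm and on the full 15% being missing. A reader might take them as an estimate of bias, but the documents give neither a responder rate nor a reason to expect that gap. If data are missing at random given the model's covariates, the two analyses would usually be close. Months 6, 9 and 12 are unaffected, and so are the non-inferiority test and the sample size.

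A reader might also infer that imputation should replace the Month 3 Fisher analysis. The documents do not support that, because Protocol 9.4.2 names Fisher's test for that visit. The imputed result belongs beside it.

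**What to change.** - **SAP 9.2.1 and 11.1:** add a Month 3 responder analysis derived from the five imputed datasets of SAP 11.6, applying the same no-change rule to re-enrolled subjects. Report the rate in each arm and the rate difference with a confidence interval, pooled by Rubin's rules. Present it next to the planned observed-case analysis with Clopper-Pearson intervals and Fisher's test.
- **Months 6, 9 and 12:** leave on observed cases.
- **SAP 15.2:** state which endpoints MI applies to and why, covering both the responder rate and the primary endpoint. If the wording of Protocol 9.6 was unintended, say so there.

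The cost is a few lines of SAP text and a small program on datasets that will exist anyway. There are two drawbacks. Fisher's test cannot be pooled directly across imputations, so the imputed result is a difference with an interval and not an exact p-value. The imputed scores are linear-model draws rounded to whole grades, and cutting rounded draws at one grade can slightly distort a proportion; a table footnote should say so.
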